Annually, approximately 15 million babies worldwide are born preterm [1, 2]. Preterm birth is a leading cause of neonatal mortality and morbidity [3]. Cervical insufficiency is one factor implicated in the complex mechanisms involved in spontaneous preterm birth [4]. Cervical insufficiency is characterized by acute and painless dilatation of cervix in absence of uterine contractions resulting in the inability of cervix to retain a pregnancy to term. Insertion of a cervical cerclage suture can be used to treat cervical insufficiency. A cervical cerclage is a mechanical support to the cervix, where a surgical band or string is applied around the cervix to prevent preterm opening of the cervix, and thereby preventing preterm birth. It can be applied either vaginally or trans-abdominally. The latter can be applied either by laparoscopic or open access surgery. Growing evidence support that both open access and laparoscopic cerclage procedures are safe and effective [5]. Still, many aspects of the abdominal cerclage remains uncertain. Recently, a study by Ades et al. was published on the obstetric outcome of subsequent pregnancies in women from an Australian single-center cohort who had a laparoscopic cerclage left in situ [6]. They reported on 22 women who became pregnant a second or third time after a laparoscopic cerclage. The authors encouraged other groups to report their obstetric outcomes on subsequent pregnancies after laparoscopic cerclage in order to gather a larger data material to describe this gap in evidence. Therefore, we plan to study the obstetric outcome from the first and subsequent pregnancies after laparoscopic cerclage in a Danish cohort from Aarhus University Hospital in a 10 years' period.

Objective

In a Danish cohort, to investigate the obstetric outcome after laparoscopic cerclage placement in the first and subsequent pregnancies.

Material and Methods

Study type

Observational study based on medical chart review.

Eligibility criteria

Women who underwent laparoscopic cerclage at Aarhus University Hospital, Denmark between May 2011 and May 2021. Trachelectomy prior to the laparoscopic cerclage is defined as an exclusion criteria.

The laparoscopic cerclage procedure

The surgical method of the laparoscopic cerclage procedure at Aarhus University Hospital is previously described in a paper by Riiskjaer et al [7]. The primary surgeon has been one of three laparoscopic surgeons with a long experience in performance of the procedure.

Variables and outcomes

Below is provided an overview of the included variables collected from the in-hospital electronical medical chart.

Demographics and obstetric history

Maternal characteristics at time of laparoscopic cerclage:

- Maternal age (years)
- Parity (reflect the number of births ≥ 22 gestational weeks)
- Body mass index (BMI) (kg/m²)
- Smoking (yes/no)
- Trachelectomy (yes/no)
- Previous caesarean delivery (yes/no)
 - If yes; Planned or non-laboring (cervical dilatation <4cm)/Laboring caesarean delivery with cervical dilatation > 4cm and <10cm/Laboring caesarean delivery at full cervical dilatation
 - If laboring; cervical dilatation prior to the caesarean section (cm)
 - If yes; indication (labour dystocia/fetal distress/maternal request/non-cephalic presentation/extensive vaginal bleeding/maternal medical complication/other)
- Previous cervical conisation (0/1/2/3 or 4)
- Previous surgery of the uterine wall (yes/no)
 - If yes; myomectomy/sepum resection/other
- Timing of laparoscopic cerclage (before conception/in early pregnancy)
 - If in early pregnancy; gestational age at cerclage placement
- Indication for the laparoscopic cerclage placement as stated by the clinician;
- in the following, the presumption is that the miscarriages/deliveries is likely to be associated with cervical insufficiency (more than one answer is allowed)
 - History of laboring cesarean delivery (>4cm dilated) followed by a spontaneous singleton miscarriage/delivery between 14+0 and 28+0 weeks
 - History of laboring cesarean delivery (>4cm dilated) followed by a spontaneous singleton delivery between 28+1 and 34+0 weeks
 - History with a prior elective vaginal cerclage but nonetheless a spontaneous miscarriage/ delivery between 14+0 and 28+0 weeks
 - History with a prior elective vaginal cerclage but nonetheless a spontaneous delivery between 28+1 to 34+0 weeks
 - History of a previous emergency cerclage with but nonetheless a spontaneous miscarriage/ delivery between 14+0 and 28+0 weeks
 - History of a previous emergency cerclage with a spontaneous delivery between 28+1 and 34+0 weeks
 - Any conization and a short pre-pregnancy cervix
 - Any conization and one or more spontaneous miscarriages/deliveries between 14+0 and 28+0 weeks
 - Any conization and one or more deliveries between 28+1 and 34+0 weeks
 - History of two or more spontaneous miscarriages/deliveries between 14+0 and 28+0 weeks

- History of two or more deliveries between 28+1 and 34+0 weeks
- History of three or more spontaneous miscarriages/deliveries between 14+0 and 36+6 weeks
- Other (free text)

Characteristics of the surgical procedure

- Additional procedures performed during surgery (e.g. hysteroscopy, removal of endometriosis)
- Performed in Day Surgery (yes/no)
- Date of surgery (dd-mm-yyyy)
- Early complications from the laparoscopic cerclage (follow-up time is 30 days from the procedure):
 - Conversion to laparotomy during surgery (yes/no)
 - Haemorrhage > 500 ml (yes/no)
 - Postoperative infection treated at hospital (yes/no)
 - Damage to internal organs (yes/no)
 - Need for re-operation (yes/no)
 - Admission to Intensive Care Unit (yes/no)
 - Thromboembolic events (defined as deep vein thrombosis, pulmonary embolism or stroke) (yes/no)
 - Maternal cardiopulmonary arrest (yes/no)
 - Maternal death (yes/no)
- Late complications from the laparoscopic cerclage (follow-up in the entire period of data collection subsequent to the laparoscopic cerclage):
 - Erosion into the vagina treated in hospital (yes/no)
 - Pain complaints from the stiches leading to intervention in pregnancy (yes/no)
 - Other complications from the cerclage leading to intervention in hospital (free text)

For every known/confirmed pregnancy subsequent** to the laparoscopic cerclage (follow-up in the entire period of data collection subsequent to the laparoscopic cerclage):*

**defined as a pregnancy confirmed by urine and/or serum hcg and/or ultrasound AND described in the medical record*

***If the laparoscopic cerclage was performed in early pregnancy, this pregnancy is the first pregnancy for data collection*

- Pregnancy;
 - Maternal age (years)
 - Parity (numerical)
 - Conceivement (Spontaneous/Assisted Reproductive Technologies)
 - Certain gestational age, defined as gestational age determined by Crown-Rump-Length (yes/no)
 - Gestation (singleton/multiple)

- Treatment with vaginal progesterone (yes/no)
- At miscarriage or delivery;
 - Gestational age (weeks and days)
 - If gestational age < 22 weeks and 0 days of gestation;
 - Need for operative surgery in connection with miscarriage (yes/no)
 - If gestational age ≥ 22 weeks and 0 days;
 - Administration of lung maturation < 34 weeks of gestation (yes/no)
 - Administration of tocolytics < 34 weeks of gestation (yes/no)
 - Chorioamnionitis (defined as antibiotic treatment or intervention leading to delivery)
- Indication for delivery (spontaneous labor contractions/PPROM/PROM/obstetric indication/abdominal cerclage as indication for delivery)

Outcomes

The outcomes of this study apply to a set of core outcomes for evaluation of interventions to prevent preterm birth leaving out the late neurodevelopmental morbidity [8].

Maternal:

- Pregnancy and delivery (follow-up in the entire period of data collection subsequent to the laparoscopic cerclage):
 - Time from the laparoscopic cerclage to first known/confirmed pregnancy (counting from the first day in pregnancy based on results from ultrasonography if available, otherwise on the date of her last menstrual period)
 - Pregnancies subsequent to the laparoscopic cerclage (numerical)
 - Miscarriages
 - Early miscarriages (< 16 weeks and 0 days)
 - Late miscarriages (< 22 weeks and 0 days)
 - Deliveries < 28 weeks and 0 days of an infant living at time of discharge from hospital
 - Deliveries < 32 weeks and 0 days of an infant living at time of discharge from hospital
 - Deliveries < 34 weeks and 0 days of an infant living at time of discharge from hospital
 - Deliveries < 37 weeks and 0 days of an infant living at time of discharge from hospital
 - Uterine rupture (yes/no)

Neonatal:

The following neonatal outcomes are reported for neonates delivered with a gestational age ≥ 20 weeks and 0 days.

- Gestational age (weeks and days)
- Birthweight (g) (follow-up at delivery)
- Neonatal survival (defined as survival at time of discharge from hospital)
- Survival with major neonatal morbidity (time point: at discharge from hospital)
 - Necrotising enterocolitis (NEC)

- Bronchopulmonary Dysplasia (BPD) (defined as respiratory/oxygen support at postmenstrual age (PMA) 36 weeks)
- Intraventricular haemorrhage (IVH) Grade III and IV
- Hydrocephalus with ventriculoperitoneal (VP) shunt
- Periventricular leukomalacia
- Retinopathy of prematurity (ROP)

Statistical analysis plan

Statistics will be descriptive and data will be presented with counts and percentages for categorical variables, mean and standard deviation for continuous Gaussian distributed variables, and median and interquartile range for continuous non-Gaussian variables. Proportions will be presented with a 95% confidence interval for the dichotomous outcomes '*neonatal survival*' and '*neonatal survival without major neonatal morbidity*'.

Subgroup analyses of the primary outcome will be undertaken for the following subgroups:

- Prior versus no prior cesarean delivery at time of laparoscopic abdominal cerclage
- Prior versus no prior conisation at time of laparoscopic abdominal cerclage
- Placement of laparoscopic abdominal cerclage before or during early pregnancy

STATA will be used for data management and analyses.

Data collection

Prior to data collection the relevant authority (Central Denmark Region) will be applied for permission to access the relevant data source. All data is already available and will be extracted from the patients' electronic data records. Women will be identified on the ICD-10 Procedure Code KLDD10B. The follow-up period extends to May 2022 to allow at least one year of follow-up for all procedures. The primary investigator performs a pilot collection of data from the electronic data records of ten random women in the data set giving birth at Aarhus University Hospital. The pilot collection aims to test the accessibility of the variables, the use of the eCRFs, and the time spent. Following the pilot of data collection, the study group meet to adjust the variables if needed.

Data management

All data will be entered in to an eCRF designed for this study using the REDCap database Study. Data will be collected and managed using REDCap electronic data capture tools hosted at Aarhus University [9]. REDCap is a secure, web-based application designed to support data capture for research studies, providing 1) an intuitive interface for validated data entry; 2) audit trails for tracking data manipulation and export procedures; 3) automated export procedures for seamless data downloads to common statistical packages; and 4) procedures for importing data from external sources.

Data will be handled according to all relevant Danish laws including the General Data Protection

Regulation (“Databeskyttelsesforordningen”) and the Data Protection Act (“Databeskyttelsesloven”). The project is registered with the Central Denmark Region’s internal list of research projects.

Publication plan

Results from this study will be published in a peer-reviewed journal.

The principal investigator will draft the paper as first author, and the daily supervisor will be last corresponding author. Additional authorship will follow standard authorship guidelines and will include all members of study group. Authorships of additional publications will depend on the nature of involvement.

Confidentiality

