## Statistical analysis plan

Statistics will be descriptive and data will be presented with counts and percentages for categorical variables, mean and standard deviation for continuous Gaussian distributed variables, and median and interquartile range for continuous non-Gaussian variables. Proportions will be presented with a 95% confidence interval for the dichotomous outcomes.

Subgroup analyses of the primary outcome will be undertaken for the following subgroups:

- Prior versus no prior cesarean delivery at time of laparoscopic cerclage
- Prior versus no prior conisation at time of laparoscopic cerclage
- Placement of laparoscopic abdominal cerclage before or during early pregnancy

STATA will be used for data management and analyses.

Examples of anticipated tables is shown below.

**Table 1.** Maternal Characteristics upon laparoscopic cerclage placement

n	n
Age, years	mean (range)
Smoking	no. (%)
Body Mass Index (kg/m  )	median (interquartile range)
Parity	median (interquartile range)
Previous conization	no. (%)
- 0	no. (%)
- 1 conus	
- 2+	
Previous caesarean delivery	
Performed as emergency caesarean	no. (%)
Previous uterine surgery	no. (%)
Placement of laparoscopic cerclage during pregnancy	no. (%)
Indications for the laparoscopic cerclage placement	
a) Previous emergency/laboring cesarean delivery followed by a spontaneous singleton late miscarriage or preterm birth from 16+0 to 28+0 weeks	no. (%)
b) Previous elective vaginal cerclage placement but nonetheless a spontaneous late miscarriage or preterm birth between 14+0 and 28+0 weeks (= failed vaginal cerclage)	no. (%)
c) Previous ultrasonography-indicated emergency cerclage with preterm birth between 14+0 and 28+0 weeks	no. (%)
d) Conization and a short pre-pregnancy cervix	no. (%)
e) Two or more deliveries in gestational age 16+0 to 28+0 weeks and a clinical diagnosis of cervical insufficiency	no. (%)
f) Three or more deliveries in gestational age 16+0 to 36+6 weeks	no. (%)
g) Others	no. (%)

**Table 2.** Characteristics laparoscopic cerclage procedure

n		n
Additional procedures performed during surgery		no. (%)
Performed in Day Surgery		no. (%)
Year of surgery		
2011 trough 2014		no. (%)
2015 trough 2018		no. (%)
2019 trough 2022		no. (%)
Early complications		
Conversion to laparotomy during surgery		no. (%)
Haemorrhage > 500 ml		no. (%)
Postoperative infection treated at hospital		no. (%)
Damage to internal organs		no. (%)

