Need for re-operation		no. (%)
Admission to Intensive Care Unit		no. (%)
Thromboembolic events		no. (%)
Maternal cardiopulmonary arrest		no. (%)
Maternal death		no. (%)
Late complications		
Erosion into the vagina treated in hospital		no. (%)
Pain complaints from the stiches leading to intervention in pregnancy		no. (%)
Other complications from the cerclage leading to intervention in hospital		no. (%)

**Table 3.** Pregnancy outcomes and neonatal survival subsequent to laparoscopic cerclage placement

Obstetric outcome in pregnancies treated with laparoscopic cerclage  
Statistical analysis plan version 1.0

**Table 4.** Time intervals

n	n
Time from the laparoscopic cerclage to first pregnancy (years and days)	median (IQR)

**Table 5.** Characteristics of live born neonates

n	n
Gestational age at birth	no. (%)
Birth weight (g)	median (IQR)

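### Late complications in SAP Table 2 are crude percentages over 1 to 11 years of follow-up, so they are not a risk at any stated time, and the pain-in-pregnancy row has no at-risk denominator

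*Protocol*

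**What the plan says.** Eligibility (Protocol, Eligibility criteria) covers "Women who underwent laparoscopic cerclage at Aarhus University Hospital, Denmark between May 2011 and May 2021". Under Data collection the protocol adds: "The follow-up period extends to May 2022 to allow at least one year of follow-up for all procedures".

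Under Characteristics of the surgical procedure, the protocol gives two observation windows. The first is fixed: "Early complications from the laparoscopic cerclage (follow-up time is 30 days from the procedure". The second is open-ended: "Late complications from the laparoscopic cerclage (follow-up in the entire period of data collection subsequent to the laparoscopic cerclage". The late items are "Erosion into the vagina treated in hospital (yes/no", "Pain complaints from the stiches leading to intervention in pregnancy (yes/no" and a free-text item for other complications. No event date is listed for any of them.

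The SAP's method is general: "Statistics will be descriptive and data will be presented with counts and percentages for categorical variables". In its Table 2 the early and late complications stand in one column under a single n, each as a number and percentage. One late row is "Pain complaints from the stiches leading to intervention in pregnancy". Neither document gives a person-time or cumulative-incidence method, a censoring rule, a summary of follow-up length, or a separate denominator for women who became pregnant.

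**The concern.** A number and percentage is a proper risk for the early complications, because every woman has the same 30 days. It is not one for the late complications, because a woman operated on in 2011 has up to ten more years in which to have an event than one operated on in 2021. The resulting figure depends on when the operations took place as well as on how often the complication occurs. Without a follow-up summary, a reader can neither interpret it nor set it beside another cohort's figure. Because the items are yes/no, the dataset as specified could not support a time-based estimate later.

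The pain row has a second problem. Only a woman who becomes pregnant can have the event. The protocol includes women operated on before conception, and some of them may have had no pregnancy by May 2022. Under the single n of Table 2, such women would count in the denominator without ever being at risk.

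**Working it through.** **Inputs.** The surgery window and the common end date come from the protocol; the layout comes from SAP Table 2. The documents give no complication rate, accrual pattern or share of women with a pregnancy. Those are assumptions below, shown as ranges.

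**Follow-up.** Shortest: May 2022 − May 2021 = 1 year, which reproduces the protocol's stated minimum. Longest: May 2022 − May 2011 = 11 years. With even accrual the mean is (1 + 11)/2 = 6 years; (11 − 5)/10 = 60% of women have at least 5 years and (11 − 10)/10 = 10% have at least 10. These are nominal figures that assume each woman stays observable to May 2022. Table 2 also has a last surgery-year band reaching 2022, while eligibility ends in May 2021. If later operations were included, the one-year minimum would fail, so the two should be reconciled.

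**What the crude percentage estimates.** If F(t) is the risk by time t, the crude proportion is the average of F(u) over the women's follow-up times u. With u uniform on 1 to 11 years and a constant hazard h, F(t) = 1 − exp(−ht), and

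crude = 1 − [exp(−h) − exp(−11h)]/(10h).

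For h = 0.005: 1 − (0.995012 − 0.946485)/0.05 = 2.95%. The 5-year risk is 1 − exp(−0.025) = 2.47% and the 10-year risk is 1 − exp(−0.05) = 4.88%.

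| Hazard per year | Crude | 5-year risk | 10-year risk | Crude ÷ 10-year |
|---|---|---|---|---|
| 0.2% | 1.19% | 1.00% | 1.98% | 0.60 |
| 0.5% | 2.95% | 2.47% | 4.88% | 0.60 |
| 1% | 5.78% | 4.88% | 9.52% | 0.61 |
| 2% | 11.16% | 9.52% | 18.13% | 0.62 |

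In every row the crude figure lies below the 10-year risk and above the 5-year risk.

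**Other hazard shapes.** Fix the 10-year risk at 3%, so H = −ln(0.97), and keep even accrual. The Weibull form is F(t) = 1 − exp(−H(t/10)^k). Risk confined to the first T years is F(t) = 1 − exp(−H·min(t,T)/T).

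| Shape | Crude | Share of 10-year risk |
|---|---|---|
| Weibull, k = 2 (late events) | 1.34% | 45% |
| Weibull, k = 0.5 (early events) | 2.25% | 75% |
| Confined to first 5 years | 2.52% | 84% |
| Confined to first 3 years | 2.80% | 93% |
| Confined to first 2 years | 2.93% | 97.5% |
| Confined to first year | 3.00% | 100% |

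When risk is confined to the first 2, 3 or 5 years, the 5-year risk is also 3%, so the crude figure falls below it. The direction against a 5-year risk is therefore not fixed.

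**Accrual.** At h = 0.005, linearly rising accrual gives mean follow-up of 4.33 years and a crude 2.14% (2.14/4.88 = 44% of the 10-year risk). Linearly falling accrual gives 7.67 years and 3.75% (3.75/4.88 = 77%). The hazard is the same in both cases, yet the reported percentage differs.

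**Pain row.** Percentage shown = true percentage among women with a pregnancy × share of women with a pregnancy. For a true 3%: 3 × 0.6 = 1.8%, 3 × 0.7 = 2.1%, 3 × 0.8 = 2.4%, 3 × 0.9 = 2.7%.

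**The case against.** The strongest reply is that the study is descriptive, its objective is obstetric outcome, and late complications sit with the procedure characteristics rather than under Outcomes. The plan nowhere calls the percentage a long-term risk, and events may be few. All of this stands and limits the weight of the point. It does not remove it: in a descriptive study the percentage is itself the result, and this one has no time reference.

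Three stronger readings are tempting, and the documents do not support them.

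- A reader might infer that long-term risk is understated. That needs a benchmark the plan does not set. Against 10 years the crude figure is too low if events occur after the first year; against 5 years it can be too high. The 60% to 62% also requires a constant hazard and even accrual, and the documents favour no hazard shape.
- A reader might infer that recent operations will look safer. Table 2 lists surgery period and complications as separate row blocks, and surgery period is not among the planned subgroups, so no such comparison is planned.
- A reader might take it as stated that the pain row is divided by all women. This is inferred from one n in a shell that the SAP offers as an example. What is established is that no separate denominator is given.

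**Conclusion.** The point holds as one of reporting and data capture. Nominal follow-up of 1 to 11 years, the lack of event dates and the single-n layout all follow from the documents. The late-complication percentages will therefore be averages of risks over unequal periods. The size of any distortion cannot be derived from the documents. With even accrual assumed, the crude figure is 45% to 100% of the 10-year risk across the shapes tried, with no shortfall only if all events fall in the first year. The pain row, read as laid out, would be lowered by the share of women without a pregnancy: 10% to 40% in relative terms for assumed pregnancy shares of 90% to 60%, and not at all if every woman has a pregnancy. The effect is confined to the safety rows of Table 2.

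**What to change.** Add two fields to the eCRF: the date of each late complication, and each woman's end of observation, with a written rule for when observation ends before May 2022. Surgery date is already collected, and the study group's meeting after the pilot is meant for adjusting variables.

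For erosion and other complications, keep n (%) and report beside it:

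- median follow-up with range;
- events per 100 woman-years with an exact Poisson 95% confidence interval;
- if events permit, cumulative incidence at fixed times, for example 1 and 5 years, with numbers at risk.

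For the pain row, woman-years from surgery are not suitable, because risk exists only during pregnancy. Use women with at least one pregnancy as the denominator and print that number in the row. Using pregnancies instead would need the item recorded for each pregnancy.

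The cost is two date fields in a chart review and a small amount of analysis. With few events the intervals will be wide. In that case the follow-up summary, the woman-year rate and the pain-row denominator are the minimum worth adding.

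### The protocol's four maternal preterm-delivery outcomes count only deliveries with an infant alive at discharge, so a delivery from 22+0 to 36+6 with no survivor is in none of the listed maternal miscarriage or delivery outcomes

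*Protocol*

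**What the plan says.** The protocol's Outcomes section, under the maternal heading, lists two miscarriage outcomes. The later one is "Late miscarriages (< 22 weeks and 0 days"), so miscarriage ends at 22+0. Four delivery outcomes follow, at 28+0, 32+0, 34+0 and 37+0. All four carry the same survival condition, from "Deliveries < 28 weeks and 0 days of an infant living at time of discharge from hospital" to "Deliveries < 37 weeks and 0 days of an infant living at time of discharge from hospital". The remaining maternal items are time to first pregnancy, number of pregnancies and uterine rupture. No maternal item covers stillbirth, death before discharge, or delivery below a cut-off whatever the infant's outcome. The list gives no denominator.

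The information does appear elsewhere in the plan:

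- Gestational age is recorded for every miscarriage or delivery after the cerclage (protocol, Variables and outcomes).
- The neonatal list is introduced by "The following neonatal outcomes are reported for neonates delivered with a gestational age ≥ 20 weeks and 0 days". It includes gestational age and "Neonatal survival (defined as survival at time of discharge from hospital").
- SAP Table 5 describes live-born neonates, and its gestational-age row is formatted as counts and percentages.
- SAP Table 3 covers pregnancy outcomes together with neonatal survival, but only its title is in the text available. The SAP presents its tables as examples.

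**The concern.** Cerclage is described in the protocol's introduction as a way to prevent preterm birth, and these four lines are the only maternal outcomes that count preterm deliveries. Each one joins an unfavourable event (early delivery) to a favourable one (survival). A low count could mean few preterm deliveries or many deaths among them, and a high count could mean more prematurity or better survival. A reader who takes the line for 37 weeks as the preterm-delivery figure will be misled whenever a preterm delivery had no survivor.

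The study is also presented as a response to authors who "encouraged other groups to report their obstetric outcomes on subsequent pregnancies after laparoscopic cerclage in order to gather a larger data material". A count meant to add to a wider body of evidence should be one whose meaning is clear without knowing how many infants died.

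**Working it through.** The plan gives no preterm rate, survival rate, expected count or denominator for these outcomes, so there is no stated figure to reproduce. The check is of coverage first, then of size on assumed values.

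**Step 1. Coverage.** Inputs, all from the protocol's maternal list: early miscarriage below 16+0; late miscarriage below 22+0; delivery below 28+0, 32+0, 34+0 or 37+0, each only if an infant is alive at discharge. Applying these six rules to every gestational day from 4+0 to 36+6 gives:

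| Gestational age | Infant alive at discharge | No infant alive at discharge |
|---|---|---|
| Below 22+0 | matches at least one outcome | matches a miscarriage outcome |
| 22+0 to 36+6 | matches at least one delivery outcome | matches none |

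The gap runs from day 22 × 7 = 154 to day 36 × 7 + 6 = 258, which is 258 − 154 + 1 = 105 days. All 105 are unmatched when no infant survives; none is unmatched when one does. A twin delivery with one survivor could still be counted under the wording.

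**Step 2. Proportional shortfall (assumed values).** Let *p* be the true proportion of deliveries from 22+0 that fall below a cut-off, and *s* the share of those with at least one infant alive at discharge. The line reports *p* × *s*, so the relative shortfall is 1 − *s*.

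| Assumed *s* | Shortfall 1 − *s* | An assumed true 10% reads | Three reported deliveries correspond to |
|---|---|---|---|
| 0.9 | 10% | 9% | 3 / 0.9 = 3.3 |
| 0.7 | 30% | 7% | 3 / 0.7 = 4.3 |
| 0.5 | 50% | 5% | 3 / 0.5 = 6.0 |

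**Step 3. Effect by cut-off (assumed counts).** Suppose the true cumulative counts below 28, 32, 34 and 37 weeks are 2, 4, 6 and 12.

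| One delivery with no survivor | Lines read | Shortfall |
|---|---|---|
| at 25 weeks | 1, 3, 5, 11 | 1/2 = 50%, 1/4 = 25%, 1/6 = 17%, 1/12 = 8% |
| at 33 weeks | 2, 4, 5, 11 | 0%, 0%, 1/6 = 17%, 1/12 = 8% |

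With small counts, one event can change the lowest cut-off a great deal.

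**Step 4. Direction.** Take an assumed 100 deliveries from 22+0, of which 20 are preterm, all with a survivor. The line for 37 weeks reads 20/100. If one term delivery had instead been preterm with no survivor, the true figure would be 21/100 and the line would still read 20/100. If one of the 20 had ended with no survivor, the true figure would stay at 20/100 and the line would read 19/100. In both cases the event is left out of the numerator. The reported figure falls only in the second.

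**The case against.** The strongest reply is that the table most likely to settle the matter cannot be read. SAP Table 3, by its title, sets pregnancy outcomes beside neonatal survival, and it may already show deliveries regardless of survival. This stands as a limit: the point can be made only about the protocol's definitions. It does not remove the point, because no visible SAP text replaces the survivor-only wording.

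Second, preterm births are visible elsewhere. The gestational-age row of SAP Table 5 may tabulate preterm live births with no condition on survival to discharge, and deaths lower the neonatal survival outcome directly. This is right as far as it goes, and a reader might wrongly infer from the four lines that such deaths vanish from the study. The documents do not support that: gestational age and survival are collected or listed. But those results are per neonate, Table 5 is confined to live births, and none of them corrects the four maternal lines.

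Third, the lines may be intended as joint outcomes, and the list is not a full partition anyway, since deliveries from 37+0 also fall in no delivery line. That is possible. A joint outcome is legitimate if labelled as one, but it should not be the only maternal count of preterm delivery.

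Fourth, the protocol counts births and deliveries elsewhere without a survival condition: "Parity (reflect the number of births ≥ 22 gestational weeks") and "History of two or more deliveries between 28+1 and 34+0 weeks". The contrast is fair but weak, because these describe obstetric history and need not share the outcome definition.

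Finally, the study is descriptive, and the protocol specifies confidence intervals only for neonatal survival and survival without major morbidity. That limits the stakes, although the SAP's sentence on intervals refers to dichotomous outcomes without naming them.

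**Conclusion.** The point holds as a defect in the protocol's outcome definitions and should be fixed. As written, a delivery from 22+0 to 36+6 with no surviving infant is in none of the listed maternal miscarriage or delivery outcomes, and none of the four lines can be read as a preterm-delivery rate. This rests on the protocol's wording alone, with the body of SAP Table 3 unseen.

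The size is unknown. The 10% to 50% range and the counts of 2, 4, 6 and 12 are assumptions chosen to show how the error behaves. If no such death occurs in the cohort, the undercount is zero.

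Two stronger readings are tempting and are not supported. A reader might infer that each such death lowers the reported preterm figure; in general it is simply not counted, as Step 4 shows. A reader might also infer that the results could not be pooled with other series; the documents do not say how other series define preterm delivery, so this cannot be established from them.

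**What to change.** In the protocol's maternal list, define the four outcomes as all deliveries from 22+0 to below 28+0, 32+0, 34+0 and 37+0, regardless of infant survival. State the denominator (pregnancies or deliveries) and count each multiple gestation once. Report survival to discharge within each threshold, saying whether it is per infant or per delivery. If the survivor-only count is wanted, keep it as an additional row labelled as such. Align SAP Table 3 with these definitions.

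The cost is new wording for four lines and a few more table rows. Gestational age, singleton or multiple status, and survival at discharge are already collected or listed as outcomes, so no new field is needed. Separating stillbirth from death before discharge would be informative but is optional, and would use a field that is not currently listed. The reported preterm figure may become less favourable.
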